8.1 Screening period

The screening period must take place within 30 days prior to enrollment and include the Visit 1 (screening) and the pre-dose assessments of Visit 2 (Day 1).

The start of screening occurs on the day the first screening assessment was performed (i.e., signature of informed consent).

8.1.1 Visit 1 (screening)

Visit 1 will be performed from 30 days to 1 day prior to enrollment. The Visit 1 date is defined as the date of the first assessment performed for the study (i.e., informed consent signature). During this visit, subject informed consent will be obtained, and assessments required for the determination of subject eligibility will be performed. These assessments may generally be performed on separate days within the screening period.

Visit 1 includes:

- After discussing the study with the investigator and after agreeing to study participation by signing the ICF, subjects will be assigned a subject number by the interactive response technology (IRT) provider. For any subject, it is the responsibility of the investigator to obtain written informed consent (subject's signature) prior to performing any protocol-mandated assessment. However, assessments performed as part of the routine care of the subject may be used to assess eligibility. The subject number will identify the subject throughout the study. In case of re-screening [see Section 8], the subject number assigned during the first screening procedure will be retained.
- Review of chronic GVHD diagnosis and assess stage and score per 2014 NIH consensus criteria [Appendix 2]
- Recording of demographics, medical history, smoking status, and disease characteristics

Confidential

- Recording of previous and concomitant medications [see Section 5.2]
- SBP/DBP
- Body weight and height
- Physical examination
- Spirometry (under the responsibility of the pulmonologist)
- DLCo (under the responsibility of the pulmonologist)
- Ophthalmological examination (under the responsibility of the ophthalmologist)
- OCT (under the responsibility of the ophthalmologist)
- Hematology, blood chemistry, serum pregnancy test for WOCBP and exploratory biomarker assessments (blood lymphocyte subsets, plasma biomarkers, exploratory biomarker samples)
- TB test
- Viral serology
- Urinalysis
- 12-lead ECG
- CXR (any CXR performed within 90 days prior to screening can be used). In case of rescreening, CXR does not need to be repeated.
- Recording of AEs/SAEs: all AEs/SAEs occurring after signing of the ICF are to be reported in the eCRF and on an SAE form, if applicable.

The investigator must check inclusion/exclusion criteria. The subject must meet all eligibility criteria to be enrolled into the study. Eligibility will be assessed again at Visit 2 before the subject is enrolled and receives study drug. The reasons for screening failure are documented in the eCRF (screening information is collected for all screen failure subjects).

8.1.2 Visit 2 Enrollment Day 1 (pre-dose)

The assessments during this visit will be divided into two parts: before (pre-dose) and after (post-dose) the administration of ponesimod. During this visit, the inclusion and exclusion criteria will be confirmed and baseline assessments will be performed and recorded.

For WOCBP, the urine or serum pregnancy test at Visit 2 must be performed at least 21 days or 7 days, respectively, after the serum pregnancy test performed at Visit 1.

All Visit 2 pre-dose assessments are mandatory and must be performed within the allowed time window (described in Section 8.1.2.1). These same assessments may concurrently also serve as the Visit 1 screening assessment, if the screening assessment was not previously performed.

8.1.2.1 Visit 2 – Day 1 – pre-dose assessments

The investigator must check all inclusion/exclusion criteria. Pre-dose assessments include:

Confidential

Assessments performed within 48 hours prior to study drug administration (pre-dose)

- Spirometry (under the responsibility of the pulmonologist)
- DLCo (under the responsibility of the pulmonologist)
- Body weight
- Chronic GVHD Activity Assessments – physician-assessed [Appendix 7 – Form A]
- Administer Chronic GVHD Activity Assessment – Patient self-report [Appendix 7 – Form B]
- Administer LSS (subject completes the questionnaire after patient self-report but prior to any clinical assessments or interaction with health care providers, preferably while waiting for their appointment)
- Hematology and blood chemistry
- Urine or serum pregnancy test for WOCBP (must be at least 21 days and at least 7 days after Visit 1 serum pregnancy, respectively)

Assessments performed on the morning of study drug administration (pre-dose)

- PK/PD samples
- Recording of change in previous and concomitant medications since Visit 1 [see Section 5.2]
- SBP/DBP (under the responsibility of the cardiac safety assessor)
- 12-lead ECG (under the responsibility of the cardiac safety assessor)
- Recording of MOC (for WOCBP only)
- Recording of AEs/SAEs: all AEs/SAEs occurring after signing of the ICF are to be reported in the eCRF and on an SAE form, if applicable.

8.2 Core Treatment Period

The Core Treatment Period consists of Visits 2 (first study drug administration) to 8 (Enrollment – Day 1, Week 4, and every 4 weeks thereafter until EOT1 / Week 24).

8.2.1 Visit 2 – Enrollment Day 1 (post-dose)

Visit 2 corresponds to the start of the treatment period (Day 1 of the study). The ECGs (pre- and post-dose), BP (pre- and post-dose), and first dose administration must be performed on the same day and define the date of the visit. This date should preferably correspond to the date of enrollment in the IRT system.

8.2.1.1 Visit 2 - Day 1 - Enrollment and post-dose assessment

If eligible, the subject should be enrolled in the study, and take the first dose of study drug. The subject must be monitored for up to 12 h post-dose. Starting at 4 hours post-dose, the cardiac safety assessor must check whether the subject fulfills the hospital discharge

Confidential

criteria [see Section 5.1.7]. Subjects may be discharged from the hospital if they meet the discharge criteria before 12 h post-dose but no sooner than 4 h post-dose [see Section 5.1.7].

Visit 2 enrollment and post-dose assessment includes:

- After confirmation of eligibility (i.e., verification of all entry criteria) by the investigator:
 - Enrollment via IRT to obtain study treatment kit number
 - Dispensing of study treatment
- SBP/DBP hourly for up to 12 h post-dose with a minimum of 4 h post-dose (under the responsibility of the cardiac safety assessor)
- 12-lead ECG hourly for up to 12 h post-dose with a minimum of 4 h post-dose (under the responsibility of the cardiac safety assessor)
- PK sampling hourly for up to 12 h post-dose with a minimum of 4 samples taken.
- Recording of AEs and SAEs. (Note: On Day 1, significant findings, which in the view of the cardiac safety assessor meet the definition of an AE and are resolved at the time of discharge of the subject, must be reported to the principal investigator and recorded directly on the Adverse Event page of the eCRF.)
- Remind WOCBP to use the MOC defined for this study. The reminders must be documented in the hospital chart and the eCRF.
- Schedule an appointment for next visit and instruct subject to:
 - bring back any blister wallets
 - not take study treatment on the day of study visit prior to coming to the site

Subjects will need to gradually up-titrate from 2 mg to 5 mg during Days 1 to 7. As there is no site visit planned until Week 4, subjects will be instructed on how to perform the gradual up-titration during Visit 2.

The subject will be instructed to contact the site if he/she has any questions or problems.

8.2.2 Visit 3 – Week 4

The visit window for this visit is \pm 3 days. The date of drug dispensing, preferably corresponding to the date of registration of the visit in the IRT system, defines the date of the visit. Hematology, blood chemistry, urinalysis, spirometry, DLCo and pregnancy tests may be performed up to 3 days prior to this visit date. The visits include:

- Recording of changes in concomitant medications
- Assessing the MOC and recording in the eCRF (for WOCBP only)
- SBP/DBP (pre-dose)

- 12-lead ECG pre-dose
- Hematology, blood chemistry (pre-dose, local and central labs)
- PK sampling (pre-dose)
- PD sampling (pre-dose)
- Urinalysis
- Urine pregnancy test for WOCBP
- Spirometry (pre-dose; under the responsibility of the pulmonologist)
- DL_{CO} (pre-dose; under the responsibility of the pulmonologist)
- Recording of AEs and SAEs
- Study medication accountability and compliance review
- IRT call and study drug dispensing
- Remind WOCBP to use the MOC defined for this study. The reminders must be documented in the hospital chart.
- Schedule an appointment for next visit and instruct subject to:
 - bring back any blister wallets
 - not take study treatment on the day of study visit prior to coming to the site.

8.2.3 Visit 4 – Week 8

The visit window for this visit is \pm 3 days. The date of drug dispensing, preferably corresponding to the date of registration of the visit in the IRT system, defines the date of the visit. Hematology, blood chemistry, urinalysis, spirometry, DL_{CO} and pregnancy tests may be performed up to 3 days prior to this visit date. The visits include:

- Recording of changes in concomitant medications
- Assessing the MOC and recording in the eCRF (for WOCBP only)
- SBP/DBP (pre-dose)
- 12-lead ECG (pre-dose)
- Hematology, blood chemistry (pre-dose, local and central labs)
- PK sampling (pre-dose)
- PD sample (pre-dose)
- Urinalysis
- Urine pregnancy test for WOCBP
- Spirometry (pre-dose; under the responsibility of the pulmonologist)
- DL_{CO} (pre-dose; under the responsibility of the pulmonologist)
- Recording of AEs and SAEs
- Study medication accountability and compliance review

- IRT call and study drug dispensing
- Remind WOCBP to use the MOC defined for this study. The reminders must be documented in the hospital chart.
- Schedule an appointment for next visit and instruct subject to:
 - bring back any blister wallets
 - not take study treatment on the day of study visit prior to coming to the site

8.2.4 Visit 5 – Week 12

The visit window for this visit is \pm 7 days. The date of drug dispensing, preferably corresponding to the date of registration of the visit in the IRT system defines the date of the visit. Spirometry, DLco, OCT, ophthalmological examination, hematology, blood chemistry, urinalysis, spirometry, DLco and pregnancy tests may be performed up to 7 days prior to or after this visit date. The visits include:

- Administer Chronic GVHD Activity Assessment - Patient self-report [Appendix 7 – Form B]
- Administer LSS (subject completes the questionnaire after patient self-report but prior to any clinical assessments or interaction with health care providers, preferably while waiting for their appointment)
- Recording of changes in concomitant medications
- Assessing the MOC and recording in the eCRF (for WOCBP only)
- SBP/DBP (pre-dose)
- 12-lead ECG (pre-dose)
- Physical examination
- Spirometry (pre-dose; under the responsibility of the pulmonologist)
- DLco (pre-dose; under the responsibility of the pulmonologist)
- OCT (under the responsibility of the ophthalmologist)
- Ophthalmological examination (under the responsibility of the ophthalmologist)
- Hematology, blood chemistry (pre-dose)
- PK sampling (pre-dose and 3 hours post-dose)
- PD sampling (pre-dose and 3 hours post-dose)
- Urinalysis
- Urine pregnancy test for WOCBP
- Chronic GVHD Activity Assessments – physician-assessed [Appendix 7 – Form A]
- Recording of AEs and SAEs
- Study medication accountability and compliance review

- IRT call and study drug dispensing
- Remind WOCBP to use the MOC defined for this study. The reminders must be documented in the hospital chart.
- Schedule an appointment for next visit and instruct subject to:
 - bring back any bottles or blister wallets
 - not take study treatment on the day of study visit prior to coming to the site

8.2.5 Visits 6 and 7 - Weeks 16 and 20

The visit window for these visits is \pm 7 days. The date of drug dispensing, preferably corresponding to the date of registration of the visit in the IRT system defines the date of the visit. Hematology, blood chemistry, urinalysis and pregnancy tests may be performed up to 7 days prior to or after this visit date. The visits include:

- Recording of changes in concomitant medications
- Assessing and recording of MOC (for WOCBP)
- SBP/DBP (pre-dose)
- 12-lead ECG (pre-dose)
- Hematology, blood chemistry (pre-dose)
- PK sampling (pre-dose)
- PD sampling (pre-dose)
- Urinalysis
- Urine pregnancy test for WOCBP (if applicable)
- Recording of AEs and SAEs
- Study medication accountability and compliance review
- IRT call and study drug dispensing
- Remind WOCBP to use the MOC defined for this study. The reminders must be documented in the hospital chart.
- Schedule an appointment for next visit and instruct subject to:
 - bring back any bottles or blister wallets
 - not take study treatment on the day of study visit prior to coming to the site

8.2.6 Visit 8 – EOT1 Visit

The EOT1 visit will take place at Week 24 (\pm 7 days) or earlier in case of premature discontinuation of study drug. In all cases, the EOT1 visit must take place 1 to 3 days after the last dose of study drug. It is strongly preferred that the EOT1 visit takes place 1 day after the last dose of study drug. Spirometry, DLco, hematology, blood chemistry, urinalysis and pregnancy tests should be performed 1 to 3 days after the last dose of study drug and do not need to be performed on the same day as the EOT1 visit. OCT and the

ophthalmological examination may be performed up to 7 days after the last dose of study drug.

The visit includes:

- Administer Chronic GVHD Activity Assessment – Patient self-report [Appendix 7 – Form B]
- Administer LSS (subject completes the questionnaire after patient self-report but prior to any clinical assessments or interaction with health care providers, preferably while waiting for their appointment)
- Chronic GVHD Activity Assessments - physician assessed [Appendix 7 – Form A]
- Recording of changes in concomitant medications
- Assessing and recording of MOC (for WOCBP only)
- SBP/DBP
- 12-lead ECG
- Body weight
- Physical examination
- Spirometry (under the responsibility of the pulmonologist)
- DLco (under the responsibility of the pulmonologist)
- OCT (under the responsibility of the ophthalmologist)
- Ophthalmological examination (under the responsibility of the ophthalmologist)
- Hematology, blood chemistry, PK/PD and exploratory biomarker assessments (blood lymphocyte subsets, plasma biomarkers, exploratory biomarker samples)
- Urinalysis
- Urine pregnancy test for WOCBP (if applicable)
- Recording of AEs and SAEs
- Study medication accountability and compliance review
- IRT call
- Remind WOCBP to use the MOC defined for this study. The reminders must be documented in the hospital chart.
- Schedule an appointment for next visit.

8.3 Core Safety Follow-up Period / Follow-up Period 1

The Follow-up Period 1 consists of the 30-day (+7 day window) post-core treatment safety follow-up visit (FU1) and the 90-day (+7 day window) post-core treatment safety follow-up visit (FU2).

The EOS visit occurs:

- At visit FU1 if a subject discontinues study drug prematurely during the Core Treatment Period.

Confidential

- At FU2 if the subject does not prematurely discontinue study drug during the Core Treatment Period.

For subjects who completed the 24 week Core Treatment Period: if such a subject enters the Extension Treatment Period prior to or on the same day of a scheduled FU1 and/or FU2 visit, then the respective FU1 and/or FU2 visits are cancelled. If these visits are cancelled then EOS occurs only after the subject completes the Extension Safety Follow-up Period [Section 8.4.5].

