1.3.2.2 Pharmacodynamics in humans

Oral administration of ponesimod dose dependently reduces the circulating lymphocyte count in humans. The maximum reduction from baseline of approximately 65–80% is achieved after a single dose of ≥ 50 mg, or at steady-state, at 40 mg o.d. The nadir in

Confidential

lymphocyte count is attained within 6–10 h following a given single dose. There is no evidence of tachyphylaxis of lymphocyte reduction. Peripheral blood counts of both T- and B-cells are reduced by ponesimod, while NK cells and neutrophils are not reduced. Food, race and/or gender do not appear to relevantly affect the PD of ponesimod. Upon discontinuation of ponesimod, the lymphocyte count generally returns to within the normal range within 1 week.

The magnitude of lymphocyte-count reductions seen with ponesimod in subjects with MS were consistent with observations made after treatments of short duration in healthy subjects. In the Phase 2 dose-finding study AC-058B201 with subjects with RRMS, at Week 24, the mean reductions from baseline in lymphocyte count were 49.8%, 65.3% and 68.6% in the ponesimod 10 mg, 20 mg, and 40 mg groups, respectively, compared to a mean increase of 3.3% in the placebo group. Lymphocyte count remained stable on treatment and returned to baseline levels within 1 week following ponesimod treatment discontinuation.

More detailed information can be found in the Investigator's Brochure [Ponesimod IB].

1.3.2.3 *Efficacy in humans*

Efficacy results are available for ponesimod in moderate-to-severe psoriasis and in RRMS.

Study AC-058A200 was a randomized placebo-controlled study, and the primary objective was to demonstrate the efficacy of 20 mg ponesimod o.d. on mean Psoriasis Area and Severity Index (PASI) at Week 6 in plaque psoriasis subjects. Although PASI improved, the primary endpoint was not achieved. PASI improved in both ponesimod and placebo groups up to Week 4; thereafter, the rate of decrease appeared more pronounced in ponesimod groups.

Study AC-058A201 was a randomized placebo-controlled study, and the primary objective was to demonstrate the efficacy of 20 and 40 mg ponesimod versus placebo at 16 weeks. There was a highly significant effect of both 20 and 40 mg doses over placebo in subjects achieving a 75% reduction in PASI score (primary analysis) and in Physician's Global Assessment of 'Clear' or 'Almost clear' at Week 16.

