3.2.2 Core Treatment Period

The Core Treatment Period starts at enrollment, which occurs at the time of first study drug intake, and continues until the end of treatment at Week 24. Visits during the treatment period will consist of an enrollment visit (Day 1) and visits at Weeks 4, 8, 12, 16, 20, and 24.

The End-of-Treatment 1 (EOT1) visit will take place at Week 24 (Visit 8) or earlier in case of premature discontinuation of study drug. In all cases, the EOT1 visit should take place not later than 7 days after the last dose of study drug.

Subjects who complete EOT1 will be subsequently treated according to local standard of care at the investigator's discretion.

3.2.3 Core Safety Follow-up Period / Follow-up Period 1

[figure not shown]
All subjects will enter the core safety follow-up period after EOT1 (Follow-up period 1), which will last for either 30 or 90 days.

The follow-up period for subjects who were prematurely discontinued lasts for 30 days after the last dose of study drug and ends with the 30-day follow-up 1 (FU1) visit. This is the End-of-Study (EOS) visit for these subjects. WOCBP must continue to use acceptable MOC during this 30-day period.

The follow-up period for subjects who were not prematurely discontinued lasts for 90 days after the last dose of study drug, and consists of the 30-day FU1 site visit and the 90-day follow-up 2 (FU2) visit, which is also the EOS visit. If the subject starts the study drug (and thus enters the Extension Treatment Period) prior to or on the day of scheduled FU1 and/or FU2, then one or both of these visits are cancelled. WOCBP must continue to use acceptable MOC during this 90-day period.

The study periods are depicted in Figure 2.

Figure 2 Study periods: Screening through Follow-up Period 1

EOT = End-of-Treatment; EOS = End-of-Study; FU = follow-up; UT 1 = 6-day up-titration; UT 2 = 4-day up-titration.

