6.1 Pharmacokinetic and pharmacodynamic endpoints

6.1.1 Pharmacokinetic evaluations

- Trough concentrations (C_{trough}) concentrations of ponesimod at Day 1, and Weeks 4, 8, 12, 16, and 20 (all samples pre-dose), and Week 24
- Ponesimod concentration 3 hours post-dose at Day 1 and Week 12

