7.3.3 Spirometry

Spirometry tests will be performed at visits indicated in Table 1. In addition, unscheduled spirometry will have to be conducted in the event of respiratory symptoms (e.g., dyspnea).

Spirometry at Visit 1 can be performed at any time during the screening period. Spirometry at Visit 2 (Day 1) must be performed within 48 hours of the visit and prior to study drug intake. At Visits 3 and 4 (Week 4 and Week 8), spirometry may be performed up to 3 days prior to the visit date and must be performed prior to study drug intake. At Visit 5 (Week 12), spirometry may be performed up to 7 days prior to the visit date and must be performed prior to study drug intake. At Visits 8 and 23 (EOT1 and EOT2), spirometry may be performed up to 7 days prior to the visit date and no later than 7 days after the discontinuation of study drug. At all other visits indicated in Table 1, spirometry may be performed 7 days prior to or after the visit date. All spirometry assessments must be performed in the morning, preferably between 06:00 and 10:00, at approximately the same time to avoid diurnal variation.

Spirometry testing will consist primarily of assessing FEV₁ and FVC. Further parameters may be explored and/or used for spirometry quality control measures.

Spirometry tests will be conducted according to the ATS/ERS guidelines [Miller 2005a, Miller 2005b, Macintyre 2005]. The pulmonary function facility will ensure that the spirometer is functioning properly and is calibrated according to manufacturer instruction and ATS/ERS guidelines. A copy of the calibrations of the day of a test must be stored as source documents in the subject charts at each subject visit, and a log of calibration results must be maintained at the site.

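### EOT1 timing rules conflict (up to 7 days versus 1 to 3 days after the last dose), so end-of-treatment spirometry, and in some subjects lymphocyte and PK values, can be taken largely off drug

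*Combined protocol and SAP*

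**What the plan says.** Timing of EOT1 relative to the last dose:

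- Synopsis (Periods) and Section 3.2.2: "In all cases, the EOT1 visit should take place not later than 7 days after the last dose of study drug".
- Section 8.2.6: "In all cases, the EOT1 visit must take place 1 to 3 days after the last dose of study drug", with 1 day strongly preferred. Spirometry, DLco, hematology, chemistry, urinalysis and pregnancy tests "should be performed 1 to 3 days after the last dose of study drug". Only OCT and the eye examination may run to 7 days.
- Section 7.3.3, for both end-of-treatment visits: "spirometry may be performed up to 7 days prior to the visit date and no later than 7 days after the discontinuation of study drug". Section 7.3.4 ties DLco to spirometry.
- Section 5.1 and Table 3 run the 20 mg course to the day before EOT1, which implies 1 day.

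EOT2 repeats the conflict: the synopsis and Section 3.2.4 allow 7 days, and Section 8.4.4 requires 3.

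On offset of effect, Section 1.3.2.2 reports: "Lymphocyte count remained stable on treatment and returned to baseline levels within 1 week following ponesimod treatment discontinuation". Section 3.3 gives 7 days for lymphocyte recovery. The amendment rationale gives 1 week for lung function, and Section 5.1.10.7 gives a few days.

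EOT1 or Week 24 values feed lymphocyte reversibility from EOT1 to FU1 (Section 6.1.2), FEV₁, FVC and DLco change and reversibility (Sections 6.2.4, 11.2.10.4.1 and 11.2.10.4.2), the Week 24 re-fit of the dose-response model (Section 11.2.7.4) and the Week 24 lung response (Section 6.3). Section 6.1.1 lists trough concentrations at Day 1 and "Weeks 4, 8, 12, 16, and 20 (all samples pre-dose), and Week 24".

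**The concern.** The 7-day and the 1-to-3-day visit rules both claim to hold in all cases, and nothing says which prevails. A spirometry session on days 4 to 7 complies with Section 7.3.3 and breaches Section 8.2.6.

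The protocol itself treats day 7 as a drug-free time point. Section 5.1.10.7 uses spirometry 7 to 10 days after premature discontinuation to judge whether a lung-function decline was due to ponesimod. One day-7 session could therefore serve both as that off-drug test and as the end-of-treatment value under Section 7.3.3.

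At stake is the on-drug reference for the reversibility summaries. If EOT1 is already off drug, the change from baseline to EOT1 is too small and so is the later recovery. Fewer subjects would also meet the entry condition for the lung reversibility summary, a fall at EOT1 of more than 200 mL and 12%.

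A separate question is whether the Week 24 PK sample can be summarised as a trough when no dose is taken at EOT1 and the interval since the last dose may exceed 24 h.

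**Working it through.** The plan states no figure to reproduce here. The check has four steps.

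**1. Do the protocol's own rules produce EOT1 visits after day 3?** Yes, in two places.

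- Section 5.1.8, scenario 5: four or more consecutive doses missed in Days 149–167 leads to discontinuation and an EOT1 visit. If the last dose is on day D and D+1 to D+4 are missed, EOT1 is at the earliest on D+4, so the 1-to-3-day rule cannot be met.
- Section 5.1.10.3: for an interruption because of liver values, discontinuation follows if values have not returned to baseline within 7 days. EOT1 then falls about 7 days or more after the last dose.

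**2. How much drug is left?** Input: terminal half-life of about 32 h (Section 1.3.2.1). Assumption: first-order decline. Concentration relative to the 24 h trough is 2^(−(t−24)/32), with t in hours since the last dose.

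- 48 h: 2^(−24/32) = 0.59
- 72 h: 2^(−48/32) = 0.35
- 96 h: 2^(−72/32) = 0.21
- 120 h: 2^(−96/32) = 0.125
- 168 h: 2^(−144/32) = 0.044

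Even a day-3 sample that complies with Section 8.2.6 is about a third of a trough.

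**3. What does that imply for the lymphocyte count?** Assumptions: linear PK, and effect following concentration without lag. An E_max curve, R(d) = E·d/(k+d), was fitted to the documents' dose-effect figures and evaluated at the 20 mg-equivalent exposure left, 20 × the fraction in step 2. Four input sets were used:

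- reductions of 30/50/65% at 5/10/20 mg (amendment rationale);
- 49.8/65.3/68.6% at 10/20/40 mg (Section 1.3.2.2);
- these two pooled;
- the planning means 1.2/0.85/0.6/0.4 × 10⁹/L (Section 11.4.2).

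For the first set, E = 103.06 and k = 11.40:

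- Day 1: 103.06 × 20/31.40 = 65.7%
- Day 3: 103.06 × 7.07/18.47 = 39.5%
- Day 7: 103.06 × 0.884/12.28 = 7.4%

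Across the four sets:

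| Days since last dose | Reduction on 20 mg | Count from a baseline of 1.2 × 10⁹/L |
|---|---|---|
| 1 | 62–67% | 0.39–0.46 |
| 3 | 39–45% | 0.67–0.73 |
| 5 | 18–25% | 0.90–0.99 |
| 7 | 7–11% | 1.07–1.12 |

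The documents do not say how many samples would be late, so the shares here are assumed. With 25% of subjects sampled on day 7 and the rest on day 1, the first set gives 0.75 × 65.7 + 0.25 × 7.4 = 51.1%, and the four sets give about 48–52%. With 50% on day 7 they give about 35–37%.

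**4. Which way does lung response move?** Ponesimod 20 mg lowered FEV₁ by about 6% on average in MS patients (amendment rationale). A late FEV₁ has recovered some of that fall and is higher. Under Section 6.3.2 a higher Week 24 FEV₁ makes lung response more likely and lung progression less likely.

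**The case against.** The windows are nested. A visit on days 1 to 3 satisfies both visit rules, and Section 8.2.6 is the more specific section, says must, and separates the tests that may run to 7 days from those that may not. For hematology it is the only section setting a test window after the last dose. This stands: a reader might infer that lymphocyte, lung and PK samples are all equally allowed to day 7, but at test level only spirometry, with DLco following it, has two windows.

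Completers dose until the day before EOT1, and at Weeks 16 and 20 subjects are told only not to dose on the day of the next visit. A completer who follows this is sampled at about 24 h. So a reader might infer that the Week 24 dose-response re-fit, trough and lung response are generally contaminated, and the documents do not support that. Late EOT1 values would come mainly from early discontinuers, whose EOT1 is generally not a Week 24 assessment.

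A further tempting reading is that every affected result is biased towards no effect. Step 4 shows the reverse for lung response. Few subjects are involved in partial lung response, because it needs a baseline FEV₁ below 70% predicted and entry excludes values below 60%.

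On PK, Week 24 is listed apart from the pre-dose samples, the time of last intake is recorded with each sample (Section 7.2.1.2), and the analysis is descriptive. Section 11 leaves derivation detail to the SAP, so a time-since-dose rule may exist there. None appears in the protocol sections on these endpoints, and Section 11.2.11.2 still groups Week 24 with the trough concentrations.

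**Conclusion.** The contradiction is real for EOT1 and again for EOT2. A value taken on days 4 to 7 is largely off drug, and by day 7 essentially so. Saying the effect is entirely gone would go slightly too far: the half-life calculation leaves a lymphocyte reduction of 7–11% at day 7, against 62–67% at day 1, assuming linear PK and no lag.

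The exposure is greatest for spirometry. For lymphocyte and PK samples it depends on a site following the 7-day visit rule, or on EOT1 coming after missed doses or an interruption. Where it occurs, EOT1-based FEV₁, FVC, DLco and lymphocyte changes and their reversibility to FU1 are understated. The size depends on an unknown share of late samples. For Week 24 lung response, a late FEV₁ would tend to favour response.

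The Week 24 PK sample is a trough only if drawn about 24 h after the last dose.

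A reader might infer that the main dose-response result is at risk. It is not: it uses pre-dose counts at Weeks 4, 8 and 12. This is an inconsistency worth correcting in secondary, descriptive and sensitivity results.

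**What to change.** Reconcile the synopsis and Sections 3.2.2, 7.3.3 and 8.2.6 to one window after the last dose, stated for the visit and for each test. Do the same for EOT2 in the synopsis and Sections 3.2.4, 7.3.3 and 8.4.4. Check the result against Section 5.1 and Table 3, scenario 5 of Section 5.1.8 and the interruption procedure in Section 5.1.10.3, since the last two produce late visits by design.

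In the SAP:

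- Use the recorded time of last dose (Sections 5.1.2.2 and 7.2.1.2) to flag EOT1 lymphocyte and lung values outside the window.
- Report the on-drug and reversibility summaries with and without the flagged values.
- Include Week 24 PK in the trough summary only when drawn about 24 h after the last dose, and list the other samples with their time since dose.

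The cost is wording and one derived variable, with no new data. A few values are set apart, mainly from early discontinuers, possibly including subjects stopped for lung-function decline. Dropping them outright would be an informative exclusion in a 30-subject trial, which is why both versions should be shown.
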